7. PLANNED ANALYSIS

At the end of phase III, propensity scores will be derived on the Phase III data set on a regional level once the data is cleaned. This propensity score analysis will be based on patients who took the prescribed treatment at least once. The propensity score model and approach with regards to missing data will be the same as the one used in the phase II and III interim analysis model for propensity score assessment (see SEAP interim analysis - propensity scores [\[5\]](#)). As described in the propensity score SEAP the same logistic regression model will be used to model the probability of receiving Dabigatran in comparison to Warfarin, i.e. high propensity scores, close to 1, indicate a higher probability of Dabigatran use.

For the main analysis based on a regional level, to reduce the potential channeling bias, asymmetric propensity score trimming will be used on the patient set with a cut-point at the 1.5th percentiles of the propensity score distribution in the Dabigatran-exposed group, i.e. Dabigatran patients with a propensity score $\leq 1.5^{\text{th}}$ percentile will be excluded, and the upper 98.5th percentiles of the propensity score distribution in the Warfarin-exposed group, such that Warfarin patients with a propensity score $\geq 98.5^{\text{th}}$ percentile will be excluded (Stürmer 2010 [\[6\]](#)). In a second step for each geographical region only those patients are regarded as comparable that lie in the region of overlap based on the asymmetrically trimmed population. This patient set is denoted as the **restricted patient set in the SEAP**.

Patients excluded from the main outcome analysis will be included in the descriptive baseline data analyses and safety analyses on ADRs and AE.

Patient disposition (enrolled patients, eligible patients, restricted patient set and matched cohort) will be summarized by antithrombotic treatment choice at baseline and by region and country (all countries but countries with $n < 200$ will only be presented in the Appendix 16.1.9.2). The disposition table will additionally show the number of patients prescribed to one specific long-term treatment at baseline who had never taken the drug.

For all patients the descriptive summary will include the proportion of patients who completed study, reasons for premature discontinuation of study (including information on availability of vital status information), proportion of patients who permanently stopped antithrombotic treatment selected at baseline (as described in [Table 6.1.2:1](#)), and the reason for permanent stop of medication, if applicable. This analysis will be done per antithrombotic treatment prescribed at baseline using the long-term treatment information.

Summary statistics for continuous variables will include the N, mean, standard deviation, minimum, Q1 (lower quartile), median, Q3 (upper quartile), and maximum value; tabulations of categorical variables will present all possible categories and will display the number of observations per category as well as percentages. The number/percentage of missing values will be present as a separate category.

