Before initiation of Phase III, regular interim analyses will be conducted during Phase II on patients initiating dabigatran and those initiating VKA at the baseline visit to evaluate the similarity of patients in these two groups. These interim analyses will occur on a regional basis, based on the number of patients enrolled (approximately once or twice a year). Once comparability regarding important baseline characteristics (known risk factors for stroke and bleeding e.g. age, gender, hypertension, diabetes mellitus, prior stroke, prior transient ischemic attack, prior bleeding and concomitant medication use) of these groups has been established and the likely amount of residual channeling bias after confounder adjustment is comparatively small, Phase III will be initiated. The main measure to determine comparability of the two treatment groups regarding their important baseline characteristics will be the overlap on the propensity score, as measured by the proportion of patients in the region of overlap of the propensity score. Patients already enrolled in Phase II will complete their visit schedule as planned. Each patient enrolled into GLORIA-AF can only participate in one phase, i.e. those patients enrolled into Phase II are not eligible to participate in Phase III. In Phase III all newly diagnosed non-valvular AF patients will be followed up for three years regardless of antithrombotic therapy treatment status.

It could turn out that Phase III cannot be conducted in the EU region; i.e. if after two years of assessing baseline characteristics of dabigatran and VKA initiators in Phase II comparability

Proprietary confidential information.

© 2014 Boehringer Ingelheim International GmbH or one or more of its affiliated companies. All rights reserved.

This document may not - in full or in part - be passed on, reproduced, published or otherwise used without prior written permission.

has not been achieved, which would preclude any meaningful comparisons, then one of the following three scenarios to assess long-term comparative outcomes will be pursued:

1. If substantial overlap is achieved, and comparability in Phase II is expected to be achieved within the following six months, i.e. overlap is expected to be very soon sufficient, then Phase II will be prolonged for six more months before entering Phase III.

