prevention at baseline. Patients who discontinue initial dabigatran treatment for stroke prevention permanently will be censored at date of last drug intake + 3 days or at first intake of other relevant chronic antithrombotic treatment for stroke prevention, whatever comes first (unless the event occurred prior to the time of censoring). A patient is considered to have permanently stopped initial dabigatran treatment if other relevant chronic antithrombotic treatment is initiated for stroke prevention or otherwise dependent on the duration of a treatment interruption (thresholds of treatment interruption duration and other details will be described in the SEAP).

C) Important outcome events / analysis of composite endpoint of stroke, SEE, vascular death, MI, life-threatening bleeds (Phase III only)

Incidence rates and cumulative risks with 95%-confidence intervals for the composite endpoint and for the individual components of the composite endpoint will be calculated. This analysis will be repeated within subgroups. Examples of subgroup variables are age, gender and stroke and bleeding risk factors. In addition the calculation of incidence rates and cumulative risks will be done stratified by chronic antiplatelet treatment. If the patients initiating dabigatran treatment for stroke prevention at baseline are comparable (in terms of important baseline characteristics) to those initiating VKA treatment, incidence rates within these two groups will also be reported.

The analysis will be based on antithrombotic treatment choice prescribed for stroke prevention at baseline and all eligible patients. Patients who discontinue initial antithrombotic treatment for stroke prevention permanently will be censored at date of last drug intake + 3 days (for dabigatran and non VKA treatments) and +6 days (for VKA treatment or combinations of VKA with other antithrombotic treatments) or at first intake of other relevant chronic antithrombotic treatment for stroke prevention, whatever comes first (unless the event occurred prior to the time of censoring). A patient is considered to have permanently stopped initial antithrombotic treatment for stroke prevention, if other relevant chronic antithrombotic treatment is initiated for stroke prevention or otherwise dependent on the duration of treatment interruption (details will be described in the SEAP).

Proprietary confidential information.

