For the main treatment groups including the total group as defined in [Table 6.1: 1](#) and for all important outcome events including the two composite outcomes incidence rates with 95%-CIs, cumulative risks, and KM curves will be calculated on the eligible patient set on the first treatment period only. Only patients from the eligible patient set that took the prescribed treatment at least once are considered. Patients who discontinue initial antithrombotic treatment for stroke prevention permanently will be censored at date of last drug intake + 3 days (for dabigatran and non VKA treatments) and +6 days (for VKA treatment or combinations of VKA with other antithrombotic treatments) or at first intake of other relevant chronic antithrombotic treatment for stroke prevention, whatever comes first (unless the event occurred prior to the time of censoring). A patient is considered to have permanently stopped initial antithrombotic treatment for stroke prevention, if other relevant chronic antithrombotic treatment is initiated for stroke prevention or otherwise dependent on the duration of treatment interruption.

The main analysis of overall incidence rates with 95% confidence intervals, cumulative risks and KM curves will be repeated for at least the following subgroups, acknowledging the limited precision given the sample size: region (1160.129 only), chronic antiplatelet treatment (1160.136 only), antithrombotic treatment, age, gender, CHADS2, CHA2DS2-VASc and HAS-BLED risk scores. A graphical (forest-plot-like) display will additionally be prepared to

summarize the subgroup results per outcome on the eligible patient set for the first treatment period only. Additional subgroup analyses might be conducted as needed.

For all important outcome events (including composite outcomes) for patients initiating VKA at baseline, and patients initiating Dabigatran at baseline, incidence rates, cumulative risks with 95%-confidence intervals will be calculated by treatment, and for a graphical comparison Kaplan Meier curves will be plotted. These statistics will be calculated on the restricted and the matched patient sets and only the first treatment period is taken into account, i.e. patients who never took the prescribed treatment will not be included.

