$$[\lambda_{\text{lower}}, \lambda_{\text{upper}}] = [\{0.5 \chi^2(\alpha/2; 2x)\}/n, \{0.5 \chi^2(1-\alpha/2; 2x+2)\}/n],$$

where $\chi^2(\gamma, r)$ is the 100 γ th percentile of a chi-square distribution with r degrees of freedom, n is the patient years under risk for the event, x is the number of patients with event, and α for (1- α) % 2-sided CIs.

Cumulative risk is defined as cumulative proportion of patients with event and will be calculated as the Kaplan-Meier estimate for failure. The Kaplan-Meier curve will be plotted. The proportion of patients with event, as well as the proportion of censored patients falling into specified intervals and the Kaplan-Meier estimate for failure will be computed for the following categories:

- ≤ 3 months
- $3 < \text{and } \leq 6$ months
- $6 < \text{and } \leq 12$ months
- $12 < \text{and } \leq 18$ months
- $18 < \text{and } \leq 24$ months
- $24 < \text{and } \leq 30$ months
- > 30 months

In the following if not stated otherwise for all analyses only patients from the restricted patient set are considered. Furthermore only the first treatment period is included (i.e. as-treated analysis) if not mentioned otherwise (like e.g. for ITT analyses).

- 1) Main analysis of composite outcome (Stroke, systemic embolism, myocardial infarction, life-threatening bleeding events and vascular death)

Acknowledging the limited precision given the sample size and the potential limitations, for the main comparison of the two treatment groups, Dabigatran and VKA, with regards to the composite outcome a multivariable Cox regression model (according to the 1160.129 and 1160.136 protocols) will be performed if those patient groups are determined to be comparable in terms of the PS analysis. The multivariable Cox regression model will include the following variables as core variables: treatment, age (<65 , $65-75$, >75), gender and the following main stroke and bleeding risk factors: prior bleed, previous stroke/TIA, previous myocardial infarction, abnormal kidney function and concomitant antiplatelets use. The following further covariates will be investigated within a model selection procedure: (sub)region, congestive heart failure, left ventricular

hypertrophy, systemic embolism, complex aortic plaque, hypertension, diabetes mellitus, PAD, CrCl, NSAID use type of AF, hepatic disease, alcohol abuse, any drug (HAS-BLED), previous OAC use (within 3 months), smoking status, and concomitant medication like antipsychotics.

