- b. The main analysis will be repeated using a different variable selection procedure resulting in a potentially different model. Here the variable selection will be based on a forward likelihood ratio selection procedure based on p-values (e.g. cut-off $p>0.2$). The core variables will be fixed and the selection procedure will only be performed for the set of further covariates listed above. Again, to account for model overfitting, another restriction will be the number of events in comparison to the overall number of degrees of freedom for all covariates included in the model. The number of degrees of freedom* 10 shall not exceed the number of events reported for the composite outcome.
- c. One further sensitivity analysis for the composite outcome will be a PS matched pair analysis (1:1 greedy nearest neighbour matching using calipers equal to, e.g. 0.2 standard deviations of the logit of the estimated propensity score, matching will be performed within region). The Cox regression model to analyse the matched data with regards to the composite outcome will be performed with only treatment as the independent variable but taking into account the dependencies within the matched pairs by including a frailty parameter into the Cox model. The balance in measured covariates will be assessed using standardized mean differences. A covariate with a difference $> 10\%$ (in absolute value) will be considered unbalanced between the two treatment groups. For these unbalanced covariates, another Cox model will be optionally performed including treatment and the residually imbalanced variables. Furthermore baseline characteristics of the matched cohort after matching will be provided.
- d. In addition, Cox regression analysis (based on the main analysis model) will be performed **without censoring at permanent discontinuation of initial antithrombotic treatment for stroke prevention (intention to treat (ITT) approach)**.
- e. Regarding the main model for the composite outcome: **An additional sensitivity analysis will be conducted to assess the effect of telephone visits on outcome event reporting rates**. For this analysis, patients will be censored if they miss more than 1

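### The overlap rule in SAP section 7 secures common support, not balance, yet SAP 7.6 plots unadjusted dabigatran and VKA curves on that set, with no balanced counterpart in study 1160.136

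*SAP*

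**What the plan says.** **Who is comparable.** SAP section 7 drops dabigatran patients "with a cut-point at the 1.5th percentiles of the propensity score distribution in the Dabigatran-exposed group" or below, and warfarin patients at or above "the upper 98.5th percentiles of the propensity score distribution in the Warfarin-exposed group". Within each region "only those patients are regarded as comparable that lie in the region of overlap based on the asymmetrically trimmed population". This is the restricted patient set. Protocol 3.1 takes as its main measure of comparability the overlap on the score, "as measured by the proportion of patients in the region of overlap of the propensity score". It gives no threshold.

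**What is shown on that set.** Protocol 7.3.1 C makes reporting of the two groups' rates conditional: "If the patients initiating dabigatran treatment for stroke prevention at baseline are comparable (in terms of important baseline characteristics) to those initiating VKA treatment". SAP 7.6 then plans incidence rates and cumulative risks by treatment for all important outcome events, and "for a graphical comparison Kaplan Meier curves will be plotted. These statistics will be calculated on the restricted and the matched patient sets". The technical specifications contain no weighting or covariate adjustment. The only refinement is a repeat stratified by chronic antiplatelet treatment.

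**Where balance is tested.** In SAP 7.6, sensitivity analysis 2)c, standardised mean differences are computed for the matched cohort: "A covariate with a difference $> 10\%$ (in absolute value) will be considered unbalanced between the two treatment groups". For the restricted set, baseline characteristics are summarised overall and by region, with no balance criterion.

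**The main comparison.** SAP 7.6 1) is a multivariable Cox model on the restricted set, run "if those patient groups are determined to be comparable in terms of the PS analysis".

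**Study 1160.136.** SAP 7.6 repeats the analyses defined on the restricted and eligible sets and does not name the matched set. Of the sensitivity analyses for the composite outcome, only (d) and (f) are kept, so (a), stratified on the propensity score, and (c), matched on it, are not done.

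**The concern.** Restricting to the overlap region is a sound support (positivity) step: it removes patients for whom the other drug was hardly ever chosen. Inside the region, one arm can still sit mostly at high scores and the other mostly at low scores. The protocol's condition for putting the two groups' rates side by side is similarity on important baseline characteristics, and the overlap rule does not test that.

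The stake is the unadjusted display. If dabigatran and VKA patients still differ in risk inside the overlap region, two Kaplan-Meier curves offered for comparison will show part of that difference as if it were a drug effect. This matters most where no adjusted estimate stands beside the curves. In SAP 7.6 3) the Cox models for stroke/SEE, all-cause death and myocardial infarction are optional. None is listed for TIA, systemic embolism alone, pulmonary embolism, vascular death or life-threatening bleeding. All the models there depend on the number of events.

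**Working it through.** The documents give no figure for imbalance before or after restriction, so there is nothing of theirs to reproduce. The check asks how much imbalance the rule can remove.

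**Inputs**
- From SAP section 7: a lower cut at the 1.5th percentile of the dabigatran scores and an upper cut at the 98.5th percentile of the warfarin scores.
- Assumed: logit score N(0,1) in VKA patients and N(d,1) in dabigatran patients, with d from 0.2 to 1.0.

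**Retention and remaining difference.** The 98.5th percentile of a standard normal is 2.17, so the restricted region runs from a = d − 2.17 to b = 2.17. With Φ and φ the normal distribution function and density:
- share kept in each arm: P = Φ(b) − Φ(a)
- VKA mean inside the region: m = [φ(a) − φ(b)] / P. By symmetry the dabigatran mean is d − m.
- mean difference left, in original SDs: D = d − 2m

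Example, d = 1.0: a = −1.17. P = 0.985 − 0.121 = 0.864. m = (0.2012 − 0.0379) / 0.864 = 0.189. D = 1.0 − 0.378 = 0.622.

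**Single covariates.** The 10% limit applies to each covariate, not to the score. If k independent covariates contribute equally to the score, each has a remaining difference of about D/√k.

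| Initial d | Kept | Score difference left (D) | Share left | Per covariate, k = 10 | Per covariate, k = 20 |
|---|---|---|---|---|---|
| 0.2 | 96% | 0.160 | 80% | 0.05 | 0.04 |
| 0.3 | 95% | 0.234 | 78% | 0.07 | 0.05 |
| 0.5 | 94% | 0.370 | 74% | 0.12 | 0.08 |
| 0.8 | 90% | 0.537 | 67% | 0.17 | 0.12 |
| 1.0 | 86% | 0.622 | 62% | 0.20 | 0.14 |

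Dividing by the SD inside the restricted set instead raises the last two columns by no more than 0.004. With unequal contributions some covariates would lie higher and others lower. A simulation of the rule with 400,000 patients per scenario, a dabigatran share of 50% or 30%, and either a normal score or one built from ten binary covariates gave similar values.

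**Effect on a crude ratio.** Suppose the true rate ratio is 1 and risk multiplies by e^g per SD of the score. The crude ratio is e^(gd) before restriction. After restriction it is

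e^(gd) × [Φ(b−d−g) − Φ(a−d−g)] / [Φ(b−g) − Φ(a−g)].

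With g = ln 1.5:
- d = 0.5: from 1.22 to 1.16
- d = 1.0: from 1.50 to 1.28 (1.5 × 0.773 / 0.904)

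With g = ln 2 and d = 1.0, the ratio falls from 2.00 to about 1.5. Both the separation and the risk gradient are assumptions.

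**With stratification.** In the same simulation, comparing within quintiles of the score in the same restricted set leaves a mean score difference of about 0.01 to 0.06 SD for initial separations of 0.2 to 1.0.

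**The case against.** The strongest reply has four parts.

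1. *The treatment effect is adjusted.* A reader might infer that the dabigatran-VKA hazard ratio is itself confounded by age, renal function or bleeding history. The documents do not support that. The main Cox model forces in age, abnormal kidney function and prior bleed, among others, and it is retained for 1160.136 with its intention-to-treat version. This stands in full.

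2. *The 10% limit is for covariates.* A reader might also set the residual standardised difference of the score (about 0.18 to 0.80) against the 10% limit and conclude that every scenario fails. That is the wrong yardstick. With 10 to 20 equal covariates, all lie inside the limit at 0.3 SD; at 0.5 SD they fall on either side of it; at 1.0 SD they exceed it. A breach is possible but not shown.

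3. *Group comparability is judged elsewhere too.* It is tempting to say that the overlap test would nearly always be passed and is the only test. But Protocol 3.1 also asks that residual channeling bias after adjustment be comparatively small, Protocol 7.3.1 A plans comparisons of each baseline characteristic, and the SAP refers the score model to a separate propensity-score SEAP. That document was not available and may hold further checks. What stands against the plan is narrower: this SAP attaches no balance criterion to the set on which the curves are drawn.

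4. *The rates are descriptive, and baseline tables are shown.* Protocol 7.2 foresees no confirmatory testing, and the sample-size section urges care. But that caution concerns chance findings across many intervals, not confounding, and the SAP itself offers the curves for comparison.

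**Conclusion.** The point holds as a weakness of labelling and presentation with a real analytic consequence. The overlap rule defines support and does not establish balance. Under the normal-score assumption it keeps about 86% to 96% of patients and leaves about 62% to 80% of the mean score difference, for assumed initial separations of 0.2 to 1.0 SD. Whether any one covariate then exceeds 10% depends on facts that the documents do not give.

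The consequence is confined to the unadjusted two-arm rates, cumulative risks and curves on the restricted set. It matters most for outcomes whose Cox model is optional or not listed, and for 1160.136, where the matched-set displays are not repeated and the stratified and matched analyses of the composite are not done. The SAP states that exclusion under the composite outcome and does not restate it for the other outcomes. Even if stratified models were run for those in 1160.136, they would give hazard ratios and not balanced rates or curves. The change is advisable and cheap; the main analysis does not depend on it.

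**What to change.** 1. In SAP section 7, state that the overlap region defines who enters the adjusted comparison, and replace the wording that regards these patients as comparable. If the separate propensity-score SEAP holds a balance criterion, cite it here.
2. Add standardised differences per covariate to the restricted-set baseline table, using the 10% criterion of 7.6 2)c, by region and for 1160.136.
3. For all important outcomes, show propensity-score-weighted or stratified two-arm incidence rates, cumulative risks and Kaplan-Meier curves beside the crude ones, in 1160.136 as well. Label the crude versions unadjusted and not for treatment comparison.

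The scores are already to be estimated, so the cost is SAP wording, some additional programming and output, and somewhat wider intervals on the weighted estimates.
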